## PROCEDURES

### Recruitment procedures

Participants will be recruited with several methods. First, the Hope Clinic maintains large databases of volunteers interested in participating in future research. Email blasts and phone calls will be made to potential volunteers from these databases. ResearchMatch, a secure online database used by researchers who are seeking volunteers and people who are interested in finding research/ clinical trial studies to participate in, will also be used as a recruitment source. Site will recruit from the Emory Healthcare Clinical Data Warehouse. The Clinical Data Warehouse is a repository that integrates data from clinical applications within Emory Healthcare, providing data needed for clinical reporting, research and operational support. Any contact made by email and or phone (refer to online engagement section for direct & SMS messaging script), recruiters will use one of the following scripts:

#### **Phone call**

Participants who are called will be greeted by the study staff. "Hello, my name is [ ]. I am calling from the Hope Clinic..." Staff will refer to Oral Consent and Pre-Screener.

#### **Email**

Hello my name is [ ] and I am from Emory University Hope Clinic. We are currently looking to enroll participants into a new study at the Emory University Hope Clinic. This study aims to understand how certain HIV medications are absorbed into different body tissues and may be considered for future HIV prevention regimens in the future.. Study visits range from two to four visits, and you will be compensated for your time of travel and inconvenience. If you or anyone you know may be interested or have any questions about this study, please contact \_\_\_\_\_ or

\_\_\_\_\_. These are the basic qualifications to participate in the study:

- You may qualify if you are:
- Age 18-49
- HIV negative man who has sex with men
- HIV transgender woman who has sex with men who is not taking hormone therapy
- Not currently taking PrEP or PEP
- Willing to undergo rectal biopsy sampling

Print and on-line ads will also be placed around Emory and other community settings. Finally, active recruitment will be conducted as outlined below with face-to-face and online engagements. [name] and co-investigators have a successful track record in recruiting MSM for their research protocols utilizing all of these methods.

Volunteer contact details are collected by conducting in person face-to-face and/or online social network engagement.

**Face- to-face engagements:** Participants may be actively or passively recruited at community venues listed below and engaged with limited information about the study and study qualifications. Recruiters will use 1 out of 2 generalized scripts when engaging with participants (please see section B below). A site contact sheet or a tablet using icapture/redcap application will be used to populate name, phone number, email address, and physical address of interested participants.

**A. Face -to- Face engagement**

- a. Community annual events attended by MSM (e.g. Pride festivals, MSM symposium, etc.)
- b. Bars and Night Clubs catering towards MSM
- c. Community organizations serving MSM
- d. Sporting events
- e. Other community venues where MSM might visit/patronize

**B. For face- to- face engagement recruiters will use one of the following scripts when interacting with participants.**

- a. "Hello, my name is \_\_\_\_\_, I am a recruiter for the Hope Clinic at Emory University. We are currently seeking volunteers to participate in one of our HIV prevention research studies. If you have a moment, would you be interested in hearing more? If not, maybe you would like to leave us your contact information to speak at another time or take one of our flyers for future reference, thank you for your time. Enjoy your day."

If contact responds affirmatively, then their contact information will be collected for a screening phone call (see phone screen script).

If contact responds negatively or does not respond, no further contact will be attempted.

**or**

- b. “We are here from the Emory University Hope Clinic. We would like to talk to you about volunteering in HIV prevention studies. There are several studies that you may be eligible for [give brief description of current studies]. If you would like further information, either I or another recruiter can give you a call at a time that’s convenient for you. Can I take your name and number? Thanks for your time.”

If contact responds affirmatively, then their contact information will be collected for a screening phone call (see phone screen script).

If contact responds negatively or does not respond, no further contact will be attempted.

**Online engagements:** Potential participants will be engaged and supplied with limited information about the study and study qualifications via paid advertisements on social media sites. All print and online advertisement copies will be submitted to the Emory IRB for approval prior to launching these activities. Interested participants will click a posted ad with an embedded hyperlink, which will redirect them to a short screener. This screener will capture information regarding eligibility, including HIV status, name, phone number and email. Recruiters will use information obtained from online screener to contact and schedule participant visits. Volunteers may also be engaged directly on social media or dating sites to assess interest in research participation. Any contact made through direct messaging, recruiters will have a generalized script (mentioned below) to follow (script can also be used for SMS contacting, as well). We will seek permission from creator/ moderator of the private website/ group, etc. before entering and interaction.

**A. Online Social Network**

- c. Dating Sites (Jack’d, Adam4Adam, Grindr, etc.)
- d. Social Network (Facebook, Snapchat, Instagram, etc.)

- e. Other online social media platforms and websites where MSM might visit/patronize

**B. Script used by recruiters when engaging by direct messaging (can be used for SMS):**

a. Hello, I am a recruiter for research studies at the Emory University Hope Clinic. We are currently looking for volunteers to participate in one or more of our HIV prevention research studies. Would you be interested in learning more?

Thank you,

\_\_ Insert Name and contact details here \_\_

If contact responds affirmatively, then their contact information will be collected for a screening phone call (see phone screen script).

b. Hello, I am a recruiter for research studies at the Emory University Hope Clinic. We are currently looking for volunteers to participate our HIV prevention research studies. All enrolled volunteers will be compensated for their time, travel, and inconvenience. Would you be interested in learning more?

Thank you,

\_\_ Insert Name and contact details here \_\_

If contact responds affirmatively, then their contact information will be collected for a screening phone call (see phone screen script).

If contact responds negatively or does not responds, no further contact will be attempted.

If contact responds negatively or does not responds, no further contact will be attempted.

c. Hello, I am a recruiter for research studies at the Emory University Hope Clinic. We are currently looking for volunteers to participate in one of our HIV prevention research studies. All enrolled volunteers will be compensated for their time, travel, and inconvenience. To learn more, please visit [www.hopeclinic.emory.edu/studies/enrolling-studies.html](http://www.hopeclinic.emory.edu/studies/enrolling-studies.html) or call [contact].

Thank you,

\_\_Insert Name here\_\_

If contact responds affirmatively, then their contact information will be collected for a screening phone call (see phone screen script).

If contact responds negatively or does not respond, no further contact will be attempted. We will recruit subjects for this protocol from existing Emory University databases of MSM who have consented to be re-contacted for future research opportunities (see below).

### Study visits

Eligible Subjects will be sequentially assigned to study arms. We will assign participants to **Pre- drug arm** (control) first. Once this arm is filled, we will enroll participants in **Arm A**. After the completion of **Arm A**, study staff will start enrollment for **Arm B**. After the completion of **Arm B**, study staff will start enrollment for **Arm C**. After the previously mentioned arms are filled, we will enroll participants in **Arm D**.

Participants may participate in more than one study arm or subgroup; however, at least 6 weeks must lapse after completion of one study arm or subgroup, before entry into another. Men who participate in more than one arm or subgroup, will not be consented again and do not have to repeat the screening visit (visit 1) when starting another arm or subgroup; they will begin the new arm at visit 2.

The consent process will be conducted in a private exam room at the Hope Clinic. Copies of the consent form for this project will not be placed in individuals' medical records since this study collects sensitive information such as HIV status and sexual orientation. All participants will be provided a copy of the signed informed consent form (ICF) upon departure.

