sequentially assigned to, the participant will be asked to return to the Hope Clinic at different time points to complete the remaining visits (visit 4 and visit 5). During visits 4 and 5, all participants will undergo blood collection (approximately 24 mL of blood will be obtained), an oral cheek swab, urethral swab, 1 pre-wet and 1 dry penile swabs, and a urine sample will be collected, some of which will be used for STI testing. Each participant will also undergo a single time-point (depending on study arm assignment—either visit 4 or 5) rectal secretion collection with swabs and wicks, a swab for rectal STI testing, and a rectal biopsy via rigid sigmoidoscopy. All participants will be asked to abstain from receptive anal intercourse for 7 days after biopsy procedures to allow the mucosa to heal.

Participants will also be asked to provide an optional single semen specimen on the day of rectal sampling to further evaluate drug levels. All biologic specimens will be transferred to CDC within 4 hours of collection for measurement of antiretroviral drug levels.

Participants may participate in more than one study arm; however, at least 6 weeks must lapse after completion of 1 study arm before entry into another. Men who participate in more than one arm will not be consented again and do not have to repeat the screening visit (visit 1) when starting another arm; they will begin the new arm at visit 2.

**Duration:** The duration of this study is 2 years. Participants will be considered ‘on-study’ for no more than 12 weeks.

**Sample size:** For this protocol we will recruit 62 HIV-negative MSM (age 18- 49) who meet eligibility criteria outlined in the protocol.

**Population:** The population to be studied in this protocol are healthy HIV negative MSM who are engaging in receptive anal intercourse (RAI) and are willing to perform study procedures. We will recruit participants through existing research databases at the Hope Clinic and the Rollins School of Public Health, through internet and paper advertisements, and community venues as is currently the process for [name] ongoing research protocols.

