### **LAY SUMMARY:**

Men who have sex with men (MSM) continue to be disproportionately affected by HIV. In 2014, MSM made up approximately 2% of the U.S. population but accounted for 70% of the new HIV infections (CDC)(2). The majority of MSM acquire HIV after exposure to the rectal mucosa through unprotected receptive anal intercourse. Pre-exposure prophylaxis (PrEP) and post-exposure prophylaxis (PEP) are recommended for MSM who may be exposed to HIV to prevent infection. Current recommendations for PrEP are to take the combination anti-HIV drug, tenofovir+emtricitabine (TDF/FTC), on a daily

basis for the duration of someone's HIV risk exposure period which could be months or years. For PEP, a three-drug anti-HIV medication is recommended within 72 hours of a possible exposure for a 28-day course. While PrEP and PEP are effective, some people find it difficult to follow the recommended regimen. Therefore, additional short-course dosing regimens for PrEP and PEP are being considered for future development. The study drug provided in this study will not protect participants from HIV or treat any active infection. This proposal seeks to understand how other anti-HIV medications, taken around the time of HIV exposure (peri-PrEP), are absorbed into different body compartments, including mucosal tissues, as they may be considered for peri-PrEP regimens in the future.

For this protocol, we will recruit 62 HIV-negative MSM aged 18-49. We plan to complete enrollment for the pre- drug (control) arm first. After the completion of the pre- drug arm, we will continue to enroll sequentially in each arm until all arms are filled (Pre-drug, then Arm A, then Arm B, then Arm C, then Arm D). All participants will provide written informed consent at the first study visit and undergo a screening medical history, physical exam, and safety laboratory tests. All biologic specimens collected will be transferred to CDC on the day of collection for measurement of drug levels.

Participants (up to n=6) enrolled in the pre-drug arm will not receive any drug. At visit 2, they will undergo blood, urine, penile swab, cheek swab, rectal swab and rectal biopsy collection.

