**Pre-Drug Arm (up to n=6; enrollment for this Arm will close once 3 men complete their biopsy visit):**

**Visit 1 (screening):** Eligible MSM will provide written informed consent, be questioned about their medical history, undergo a physical exam (conducted by a study clinician) a rapid HIV test, and a peripheral blood sample for a complete blood count, creatinine, coagulation test, and hepatitis B. Participants will then be asked to return within 1- 6 weeks for visit 2.

**Visit 2:** Visit will occur within 1-6 weeks after the screening visit. Approximately 24 mL of blood will be drawn, an oral cheek swab, 1 pre- wet penile swabs and 1 dry penile swab, and a urethral swab will be collected. After previous swab collections are complete, participants will be asked to provide a urine sample, some of which will be used for gonorrhea and chlamydia testing, then the practitioner (Principal investigator or

TITLE OF PROJECT: On-Demand PEP  
Emory IRB  
PRINCIPAL INVESTIGATOR: [name], MPH

Co- investigator) will collect rectal secretion samples by using two swabs and insert an aptima swab for rectal gonorrhea and chlamydia testing, before the participant undergoes a rectal biopsy via rigid sigmoidoscopy.

Participants will be asked to provide an optional single semen sample, which will be collected at home, no more than 2hrs prior to or after the biopsy visit.

After 3 men complete the pre-drug arm, subsequent participants will be sequentially assigned to Arm A, B, C or D.

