**Group A.1 (n=8; enrollment will close once 4 men complete their biopsy visit):**

**Visit 1(screening):** Eligible MSM will provide written informed consent, be questioned about their medical history, undergo a physical exam (conducted by a study clinician) a rapid HIV test, and a peripheral blood sample for a complete blood count, creatinine, coagulation test, and hepatitis B. Participants will then be asked to return within 1- 6 weeks for visit 2.

**Visit 2:** Participants will be given a one- day supply of Genvoya®. Staff will provide instructions to participant on when to take dose at home. Participants will be asked to dose **24hrs before visit 3** and will be instructed to photograph or videotape themselves taking dose with the timestamp included with their smartphone. Study staff will instruct participants to bring the photo/video to their next visit to provide proof of dosing. Participants will also have the option to send a text to a specified number with the time and date of dose if their phone device does not have video/photo capabilities.

**Visit 3:** Visit 3 takes place 24hrs after home dose. During this visit, drugs will be dispensed to participants, and they will be instructed to take one dose of Genvoya®. Men will be dosed on-site (time of dose will be recorded) and asked to return in 2hrs. Procedures should be done as close to 2hrs as possible with a +/- 1 hour window.

**Visit 4:** Visit 4 takes place 2hrs (+/- 1 hour) after on-site dose. Approximately 24 mL of blood will be drawn, an oral cheek swab, 1 pre- wet penile swabs and 1 dry penile swab, and a urethral swab will be collected. After previous swab collections are complete, participants will be asked to provide a urine sample, some of which will be used for gonorrhea and chlamydia testing, then the practitioner (Principal investigator or Co- investigator) will collect rectal secretion samples by using two swabs and insert an

aptima swab for rectal gonorrhea and chlamydia testing, before the participant undergoes a rectal biopsy via rigid sigmoidoscopy.

Participants will be asked to provide an optional single semen sample, which will be collected at home, no more than 2hrs before/after to biopsy visit.

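### Men who re-enter another arm or subgroup start at visit 2 with scheduled HIV and safety results at least 7.0 weeks old, against a 1–6 week visit window for a first entrant, and no repeat is required

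*Combined protocol and SAP*

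**What the plan says.** Under Study visits, a man may join a second arm or subgroup provided "at least 6 weeks must lapse after completion of one study arm or subgroup, before entry into another". Men who do so "do not have to repeat the screening visit (visit 1) when starting another arm or subgroup". The Abstract repeats the waiver: they "do not have to repeat the screening visit (visit 1) when starting another arm; they will begin the new arm at visit 2".

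In every arm the rapid HIV test, blood count, creatinine, coagulation and hepatitis B tests are listed at visit 1 only. Visits 2 to 5 list dosing, drug-level specimens and, at the biopsy visit, gonorrhea and chlamydia tests. For first entrants the step from visit 1 to visit 2 has a window. For the Pre-drug arm: "Visit will occur within 1-6 weeks after the screening visit". For Group A.1, and in the same terms for the other drug groups: "Participants will then be asked to return within 1- 6 weeks for visit 2".

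Arms fill in order, Pre-drug first. For Arm D the text reads "After the previously mentioned arms are filled, we will enroll participants in" that arm, so nothing follows it. Every re-entry after a completed arm is therefore into a drug arm, with two Genvoya doses and one set of 8–10 biopsies.

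The section Risk of Genvoya provides for HIV testing at study entry and clinical monitoring at study visits. The antibody test is repeated if high-risk behaviour or symptoms of acute infection are reported.

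**The concern.** Exclusion criterion 4 makes haemoglobin, PTT/INR, platelets, creatinine clearance and HBsAg conditions of entry, assessed at baseline. A re-entrant has no new baseline at which they are assessed. He goes on to dosing and biopsy on results that are always older than those of a first entrant who keeps to the visit window.

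HIV status is the item most likely to change. The inclusion criteria select men who report receptive anal sex in the last 6 months and who do not take PrEP. The protocol gives testing at study entry as part of its answer to the theoretical concern about resistance when an infected man takes intermittent doses. For a man from the Pre-drug arm, where those "enrolled in the pre-drug arm will not receive any drug", re-entry brings his first Genvoya doses on an HIV result at least 7 weeks old. For a man from Arms A–C it brings two more doses. These are volunteers who, by the Benefits section, gain nothing directly, so a cheap safeguard is worth having.

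**Working it through.** **Inputs**

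- Visit 1 to visit 2, first entrant: 7–42 days (Pre-Drug Arm; Group A.1 and the other groups).
- Home dose to visit 3: 24 h.
- On-site dose to visit 5: 48 h (A), 72 h (B), 96 h (C).
- On-site dose to visit 4, which is the biopsy visit for A.1, B.1 and C.1: 2 h, 4 h, 24 h.
- Minimum gap before another arm or subgroup: 42 days (Study visits).
- Assumptions: the home dose is taken on the day of visit 2, and entry to the new arm means its visit 2. The ±1 h windows move the results by less than 0.01 week.

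**First entrant.** The age of results at visit 2 is read directly from the text: 7–42 days, or 1–6 weeks. The latest biopsy within the window is C.2 with visit 2 at day 42: 42 + (24 + 96)/24 = 47 days = 6.7 weeks.

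**Re-entrant.** Minimum age at the new visit 2 = 7 days + length of the earlier arm from its visit 2 + 42 days.

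| Earlier arm or subgroup | Completion taken as | Sum (days) | Weeks | Excess over 6 weeks |
|---|---|---|---|---|
| Pre-drug | visit 2 | 7 + 0 + 42 = 49 | 7.00 | 1.0 |
| A | visit 5 | 7 + 1 + 2 + 42 = 52 | 7.43 | 1.4 |
| B | visit 5 | 7 + 1 + 3 + 42 = 53 | 7.57 | 1.6 |
| C | visit 5 | 7 + 1 + 4 + 42 = 54 | 7.71 | 1.7 |
| A.1 | biopsy visit | 7 + 1 + 2/24 + 42 = 50.08 | 7.15 | 1.2 |
| B.1 | biopsy visit | 7 + 1 + 4/24 + 42 = 50.17 | 7.17 | 1.2 |
| C.1 | biopsy visit | 7 + 1 + 1 + 42 = 51 | 7.29 | 1.3 |

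The visit 5 rows fit the arm-level text better, since 8 men must complete all visits in each of Arms A–C. The biopsy rows apply if the subgroup closing rule defines completion. For A.2, B.2 and C.2 the biopsy is at visit 5, so the two readings agree.

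**At biopsy.** The earliest re-entry biopsy is Pre-drug followed by A.1: 49 + (24 + 2)/24 = 50.08 days = 7.15 weeks. Against the latest first-entry biopsy the difference is 50.08 − 47 = 3.08 days.

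**Above the floor.** These are minima, reached with a 1-week first screening interval and a gap of exactly 6 weeks. With a 6-week screening interval the same sums give 84 days (12.0 weeks) after Pre-drug, and 87, 88 and 89 days (12.4, 12.6 and 12.7 weeks) after A, B and C.

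**The case against.** The strongest reply is that 1–6 weeks is a window for the return visit and not a validity period for laboratory results. That stands. No section says that a result expires. The Contingency visit text only keeps extra visits, such as those for lost or inconclusive screening results, inside the visit windows. The waiver is stated twice and looks deliberate. The comparison shows that the plan accepts older results from re-entrants than from first entrants, and no more than that.

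The second reply is that the guaranteed difference is small. That also stands: 1.0–1.7 weeks at visit 2 and about 3 days at biopsy. The documents give neither the number of re-entrants nor the chance that a result has changed. The protocol calls the resistance concern theoretical, a hepatitis B flare unlikely and serious biopsy complications rarer than 1 in 5,000.

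Third, HIV is partly covered. Re-entry visit 2 is a study visit, so risk and symptoms are to be asked about there. Men are also asked to abstain from receptive anal intercourse while on the study, and staff are free to repeat tests. This holds only in part. The HIV re-test depends on self-report, no repeat is obligatory, and none of this covers the laboratory limits in exclusion 4. One could read study entry as each arm entry, but re-entrants start at visit 2, where no HIV test is listed.

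Fourth, the Abstract counts men as on study "for no more than 12 weeks". A single participation takes at most 47 days (6.7 weeks) on the assumptions above, so the limit may well be meant to cover re-entry. On that reading results would stay under 12 weeks. This bounds the upper end but leaves the 7.0-week floor unchanged.

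**Conclusion.** The concern holds as a modest safety gap. A re-entrant's scheduled HIV and safety results are at least 7.0 weeks old at his new visit 2. They are at least 7.4–7.7 weeks old after Arms A–C if completion means visit 5, or about 7.2–7.3 weeks for A.1, B.1 and C.1 if it means the biopsy visit. The first-entrant window is 1–6 weeks. The figures assume home dosing on the day of visit 2, and every alternative considered stays above 6 weeks. The weight is minor to moderate: a cheap improvement, not a fatal flaw.

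A reader might infer three stronger things that the documents do not support:

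- That re-entry breaches a limit on the age of results. There is no such limit.
- That men would routinely be dosed on results about half a year old. A man in every arm would reach Arm D visit 2 at 187 days (26.7 weeks) at the earliest: 49 days at A, then 3 + 42, 4 + 42 and 5 + 42. That needs the 12-week limit to apply to each participation separately, and nothing says such a path is expected.
- That the pharmacokinetic results are compromised. Nothing here bears on them.

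**What to change.** In the Abstract and under Study visits, keep the waiver of repeat consent but replace the waiver of visit 1 testing with two requirements:

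- A rapid HIV test at the re-entry visit 2, with a negative result before Genvoya is dispensed.
- A repeat of the blood count, creatinine, coagulation and HBsAg tests from a draw of about 15 mL late in the 6-week gap, with results reviewed against the exclusion limits before dosing or biopsy.

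The timing of the HIV test matters. A rule that accepted any test within 6 weeks of the new visit 2 would, at the minimum gap, admit one taken on the last day of the earlier arm, and so miss the whole interval of interest.

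The cost per re-entry is one finger-stick or draw of a kind already in the protocol, and at most one payment of $25, the visit 1 rate under Compensation. Laboratory cost is not given. Because the draw falls within a gap that the plan already requires, re-entry need not be delayed. An occasional man will fail a test and not re-enter. He can be replaced within the cap of 8 for each subgroup (8 for Arm D), since enrolment closes only when 4 have completed the biopsy visit.
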